# 4.3. Equality and Diversity

This trial aims to recruit an ethnically and socially diverse trial population and will adhere to the INCLUDE guidelines outlined by the NIHR.

\* Where centres routinely see the majority of partners providing sperm with normal sperm morphology ≤2%, their processes for assessing morphology will be verified to ensure they are correctly following WHO guidelines alongside the External Quality Assurance (EQA) provided through Sub-study 2: Healthcare Science.

Couples who do not speak English will be screened and approached. Written information will be translated by an interpreter, reinforced by video content in multiple languages. This has been found to be a more engaging and reliable way for couples to give true informed consent based on the trial team's clinical experience and from PPI feedback. Interpreters must also be available to facilitate the informed consent process for participants who don't speak English. This has been found to be a more engaging and reliable way for couples to give true informed consent based on the trial team's clinical experience and from PPI feedback.

Interpretation services (either available within the clinic or a medical specialist interpreter/translation company) will be available for the RCT and for the qualitative studies.

A separate trial-specific plan for achieving and maintaining equality and diversity in trial participation, PPI and public engagement will be followed throughout the study.

### 4.4. Co-enrolment

Co-enrolment may have an impact on outcomes and pose challenges to the participant pathway on both research studies. Due to this, co-enrolment will be considered on a case-by-case basis by the Trial Management Group (TMG). In all instances, the recruiting centre should contact the UNiTY Trial Office prior to offering the second trial, or before approaching a couple about UNiTY who are already enrolled into another study.

5. CONSENT

Consent for the UNiTY trial is given by both partners in the couple before any trial procedures take place. This will be gained following all HFEA Code of Practice or other recommendations that apply. One form must be completed by each partner, which can be done online (either in person or remotely) or on paper.

It is the responsibility of the Principal Investigator (PI) to ensure that informed consent is obtained for each partner prior to performing any trial related procedures. This task can be delegated by the PI to other members of the local research team, if local practice allows and this responsibility has been documented in the site signature and delegation log.

Both an Illustrated Participant Pathway and Participant Information Sheet (PIS) will be provided to facilitate this process. The PI or delegate will ensure that they adequately explain the aim of the trial, the trial intervention, and the anticipated benefits and potential hazards of taking part in the trial to the couple. They will also explain that participation is voluntary and that the couple is free to decide to take part and may withdraw from the trial at any time. The couple will be given sufficient time to read the PIS, ask any questions and discuss their participation with others outside of the site research team. As described in section 4.3, couples for whom English is not their first language will have information and consent forms provided to them, and access to an interpreter who can facilitate explaining the trial to the couple.

For all participants receiving trial treatment, details of the informed consent discussions will be recorded in their medical notes. This will include date of discussion, the name of the trial, summary of discussion, version number of the PIS given to couple, version number of the ICFs signed and date consent received. Where consent is obtained on the same day that the trial related assessments are due to start, a note should be made in the medical notes as to what time the consent was obtained and what time the procedures started.

At each visit the participant who is receiving trial treatment will have their willingness to continue in the trial ascertained and documented in the medical notes. Throughout the trial the couple will have the opportunity to ask questions about the trial. Any new information that may be relevant to the participant's continued participation will be provided. Where new information becomes available which may affect the participant who is receiving treatment's decision to continue, participants will be given time to consider and if happy to continue they will be re-consented. Re-consent will be documented in the medical notes. The participant's right to withdraw from the trial will remain.

Electronic copies of the PIS and ICF will be available from the Trial Office and will be localised to the headed paper of the local institution if paper copies are used. Audio information will be made available in multiple languages.

We will also add additional statements to the ICF for the participant to acknowledge that they understand that the Trial Office might in the future, for other related research, collect participant data available in NHS routine clinical datasets, including primary care data (e.g., Clinical Practice Research Datalink, The Health Improvement Network, QResearch) and secondary care data (e.g., Hospital Episode Statistics) through NHS Digital and other central UK NHS bodies. The participant will acknowledge that they understand that the Trial Office might send their name, address, date of birth and NHS number to the relevant national registry, and then for the national registry to link this to their data and send the information back to the Trial Office. The acknowledgement by the participant will also allow access to other new central UK NHS databases that will appear in the future. This will allow us (subject to receipt of additional funding via another grant application) to assess longer-term impact and health service usage data without needing further contact with the trial participants.

### **Online consent**

Given most couples will be used to completing documents online, this is expected to be the primary method used to obtain informed consent for couples entering the UNiTY trial. If, after discussion with the research team, the couple would like to take part in UNiTY, they will both be asked to provide their email addresses in order to complete the online consent process. A link to the REDCap database https://bctu-redcap.bham.ac.uk/ will then be emailed to both partners for them to complete online the latest version of the Informed Consent Form (ICF). Each partner will sign and date their respective consent form; once completed these will also be signed and dated by the consenting clinician. If electronic consent is preferred, a simple typed signature is acceptable within the guidelines of the MRC Joint Statement on Consent. There will be details on the online PIS on how to contact the research team if they have any further questions.

A completed consent form is saved as a pdf on the database, which can only be seen by site staff and the central trial team. This pdf can be downloaded for filing in the egg providing partner's medical notes, and copies are automatically emailed to the participants. Documentation of online consent will be evidenced by printed copies of the ICF filed in the Investigator Site File (ISF). The site team can review the forms and contact the couple if there are any questions or concerns with form completion. All screened potential participants are assigned a Couple Trial ID which is used as their unique trial identifier throughout the trial.

### Paper consent

This process will be available in case online consent is not an option for couples. The couple will be given the opportunity to ask questions before initialling, signing and dating the latest version of their respective ICF. The PI or delegate will then sign and date the ICF. Each participant will be given a copy of their ICF, copies will be filed in the medical notes and the originals placed in the ISF. Data from ICFs will be uploaded on the REDCap database for electronic review. Once the couple is enrolled into the trial, their Couple Trial ID will be entered on the ICF maintained in the ISF.

\_\_\_\_\_

# 6. ENROLMENT, RANDOMISATION and BLINDING

# 6.1. Identification and approach

Potential participants will be identified via review of medical records by clinicians and nurses within (HFEA) licenced fertility treatment centres. Couples with potential unexplained infertility will not be screened until all their investigations have been completed and a diagnosis of UEI has been confirmed. Eligible potential participants will be approached about the trial by members of their direct care team including clinic doctors and staff at assisted conception units who are responsible for their care and who are named on the local delegation log. As HFEA guidelines prohibit fertility doctors from approaching patients relating to trial participation, research nurses are in this context considered part of the direct care team subject to local confirmation.

### 6.2. Screening and enrolment

Enrolment will take place upon confirmation of eligibility and after informed consent of both partners of the couple has been obtained. Details of all couples approached about the trial will be recorded on the screening CRF; which is stored on the REDCap database and accessible by the Trials Office.

### 6.3. Couples self-funding IVF

After screening, couples who are self-funding must have paid the fertility centre for IVF treatment before they can be randomised into the trial. This is to ensure that they have the funds available as per the eligibility criteria. If the couple is randomised to receive IUI, the payment will be retained in case it is needed to fund IVF after trial treatment is completed. If the couple do not go on to have IVF the funds will be returned to them.

#### 6.4. Randomisation

Randomisation will be provided by BCTU using a secure online system (available at https://bctu-redcap.bham.ac.uk/). Unique log-in usernames will be provided to staff who wish to use the online system and who have been delegated the role of randomising participants into the trial as detailed on the UNiTY Site Signature and Delegation Log. Database users will be emailed a link to complete their account set-up including setting up their passwords. These unique log-in details must not be shared with other staff and in no circumstances should staff at sites access the system using another person's login details. The online system will be available 24 hours a day, 7 days a week, apart from short periods of scheduled maintenance. It is important to note that the time between randomisation and treatment will (at a minimum) be a number of days as consent for the relevant treatment regime will need to be taken after randomisation and before treatment can start, according with the HFEA Code of Practice. Therefore we do not expect temporary unavailability of the online system to negatively impact trial procedures.

### **6.4.1.** Randomisation process

After eligibility has been confirmed, informed consent has been given and, if applicable, payment has been received, the participant can be randomised into the trial using the online system. All questions and data items on the online Randomisation Form must be answered prior to a potential participant being randomised into the trial. The couple should only be randomised if (in the opinion of the site PI) there is a high likelihood of treatment starting (defined as date of ovarian stimulation) within 3 months of randomisation in both groups.

Following randomisation, a confirmatory email will be sent to the research team at the relevant HFEA licenced fertility treatment centre and the UNITY Trial Office.

The couple do not need to be present for the randomisation process. In this case, it is the responsibility of the local research team to notify the couple of their allocation and how they proceed on that treatment pathway.

The local research team should add the participant to the UNiTY Participant Recruitment and Identification Log which links participants with their Couple Trial ID. PIs or their delegates must ensure this document is stored securely and it must not be submitted to the Trial Office. The UNiTY Participant Recruitment and Identification Log should be held in strict confidence.

### 6.4.2. Randomisation method

Couples will be randomised at the level of the individual in a 1:1 ratio to either three cycles of IUI or one cycle of IVF.

A minimisation algorithm will be used within the randomisation system to ensure balance in the intervention allocations over specific characteristics of the partner providing the eggs and randomising centre. The following variables will constitute the minimisation variables:

- (i) Ethnicity of the partner providing the eggs (Asian, Black, Mixed, White, Other)
- (ii) BMI of the partner providing the eggs (19.0-24.9, 25.0-29.9, 30.0-34.9 kg/m^2)
- (iii) Age of the partner providing the eggs (<35, 35-37, ≥38 years), and
- (iv) Randomising centre.

To avoid the possibility of the intervention allocation becoming predictable, a random element will be included in the minimisation algorithm. Full details of the randomisation specification will be stored in a confidential document at BCTU.

### 6.5. Blinding

Due to the differing natures of the intervention, it is impossible to blind either the care providers, investigators or participants to their allocated group. While we cannot completely rule out some element of behaviour change (and hence performance) bias due to knowledge of allocated interventions, we expect the extent of such bias to be relatively small given the nature of the treatments. We have a strict, objective primary outcome, so we do not expect detection bias to be a factor.

# 6.6. Informing the participant's GP and other parties

If the participants have agreed, the GP of the participant providing the eggs should be notified that they are in the trial, using the UNITY GP Letter.

# 7. TRIAL INTERVENTION

#### 7.1. Trial interventions and schedule

Both interventions should start no more than 3 months after randomisation which should be sufficient time to complete treatment consent forms, for relevant medication to be ordered and appointments to be scheduled.

#### 7.1.1. IUI strategy

#### **Ovarian stimulation**

IUI with the aromatase inhibitor letrozole will be commenced at a dose of 5mg (2 tablets) once daily from day 2 − day 6 after commencement of period. Follicular tracking will be according to local protocol, but this is usually commenced around day 10 − day 12 using transvaginal ultrasound. When at least one follicle reaches a diameter of ≥17mm, ovulation triggering using human chorionic gonadotrophins should be administered. This will ensure that IUI can be performed at a planned time convenient to the patient and staff. Luteal support will be provided according to local protocols.

#### Insemination

Single insemination should be planned 24-40 hours post the ovulation trigger injection (33, 34). Patients will be advised to have 10-15 min bed rest after the insemination is performed (35). Protocols will be managed according to local policy to minimise the chance of multiple pregnancy. Where no policy exists (e.g. in clinics with no current IUI provision), the suggested policy will be that when more than 2 follicles >15mm are present at the time of HCG triggering, the cycle should be cancelled and the couple advised to refrain from unprotected intercourse.

# Multiple cycles

Couples who do not have a baby (due to negative pregnancy test or subsequent pregnancy loss) after their first or second cycle of IUI will proceed to another cycle. The timings for when to start this will be a decision for the couple after consultation with a clinician.

If a couple has not completed 3 cycles of IUI at the conception measurement point of 450 days post randomisation, they will no longer be able to take up those additional cycles.

# **Subsequent IVF**

While not part of the trial intervention, all couples who are not pregnant after three cycles of IUI or 270 days (nine months) post-randomisation will be offered a cycle of IVF as part of clinical care.

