# 1.1.4 Research trial proposed

There is a great deal of uncertainty regarding IUI versus IVF. Stimulated IUI, if effective, is potentially an attractive option for many couples and for ICBs because it is lower risk, less invasive and possibly more cost effective.

The UNiTY trial is a multi-disciplinary, multi-centre randomised controlled trial (RCT) designed to answer the question of whether IUI is an effective and cost-effective alternative to IVF for UEI in an ethnically and socially diverse UK population. In line with the new Medical Research Council (MRC) (NIHR) framework for developing and evaluating complex interventions, UNiTY will assess feasibility, value for money, safety and patient acceptability throughout the process. The potentially unreliable result of semen analysis is a significant factor in defining UEI and therefore trial entry. Inter-centre quality assurance of sperm analysis therefore forms a cornerstone of our trial and is a necessity to allow for the diversity of practice across the UK.

The intervention is the policy of offering three cycles of letrozole-stimulated IUI and the comparator is the policy of offering one cycle of IVF with standard ovarian stimulation and the first fresh and / or frozen embryo transfer. We will initially assess outcomes 19 months post-randomisation, when we anticipate couples will have been treated with their first IVF cycle or three cycles of stimulated IUI and subsequent pregnancy outcomes obtained. As we expect all couples unsuccessful after three cycles of IUI will proceed to at least one cycle of IVF, we will also collect and assess this data up to 25 months post-randomisation (treatment with further IVF cycles in either group will be dependent on local policy, if further NHS funding is available in a locality to a couple this will also be recorded). Within all cycles in the IVF pathway, the number of surplus frozen embryos will be documented as this can clearly inform of potential cumulative pregnancy rates — which could later be followed-up in future investigations.

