#### 7.3. Intervention modification or discontinuation.

All patients receiving off-protocol treatment will remain in the study. Data will continue to be collected from the couple until the end of their study duration. Any fertility treatment accessed by participants after completion of trial treatments is not considered a protocol deviation.

To minimise the multiple pregnancy risk, when more than 2 follicles >15mm are present at the time of HCG triggering, IUI should be withheld (17), this will be recorded in the trial as one of the three attempts as this again pragmatically reflects what would occur in current practice.

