### 7.6. Adherence

The primary analysis will examine treatment policy (all randomised participants regardless of adherence to intervention), but further analysis will investigate the intervention effect within the population of adherent couples (see Section 14). For this purpose, the adherent population will be defined as receiving three cycles of IUI (or one or two cycles if pregnant from earlier cycles) with no further fertility treatment in the IUI strategy group and one cycle of IVF with no further fertility treatment in the IVF strategy group.

Adherence to intervention will be monitored via periodic data review performed by TMG, DMC and TSC.

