#### 8.2. Main trial outcomes

#### 8.2.1. Primary outcome

The primary outcome is the live birth of a baby at ≥34 week's gestation, conceived within 270 days of randomisation (approximately 9 months). Date conceived is determined as date of egg collection for couples who have undergone fresh embryo IVF, date of embryo transfer minus the number of days of culture for couples who have undergone frozen embryo IVF, date of insemination for couples who have undergone IUI, and 14 days after the first day of the last period for couples who have conceived naturally.

In line with the evaluation of treatment policy, initial or subsequent pregnancies may be included within this timeframe. This outcome will be assessed at 19 months post-randomisation.

\_\_\_\_\_\_

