## Additional notes on Error! Reference source not found.

- Months 2-6 are an approximation for when couples will have the three cycles of IUI; this process may be longer.
- X Couples randomised to IUI but progress to IVF as part of clinical care. All couples randomised to IUI cannot progress to subsequent IVF treatment until 270 days (approximately 9 months) post randomisation.
- X to measure outcomes for all couples who conceive within 450 days of randomisation.
- X³- one Clinical Pregnancy Outcome CRF to be completed per positive pregnancy test.
- X- to be completed for each pregnancy conceived during the trial outside of IVF or IUI treatment.
- X one Post-Treatment CRF to be completed 8 weeks after treatment starts (defined as the first day of ovarian stimulation).
- The qualitative sub-studies will approach participants at the indicated timepoints, but their interviews will happen in the subsequent weeks.
- X- measured during the first treatment cycle of IUI and/or IVF. The ideal timepoint during a treatment cycle to collect these questionnaires is between the date of insemination and the date of the pregnancy test for couples undergoing IUI, and between the date of embryo transfer and the date of the pregnancy test for couples undergoing IVF.

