# Table 9: Proposed analysis populations for primary outcome of live birth≥34 weeks

Timeframe	270 days o	270 days of randomisation (primary)					450 days of randomisation (medium term)				
Group=3 cycles of IUI	1					1					
	Conceived			Not conce	ived	Conceived	Conceived			ved	
	<=3 cycles 	With further intervention (IUI, IVF, FET)	Natural pregnancy	At least 3 cycles	<3 cycles	<=3 cycles	With further intervention (IUI, IVF, FET)	Natural pregnancy	At least 3 cycles	<3 cycles	
Primary: Intention-to- treat any pregnancy 	Yes	Yes	Yes	Yes	Yes	Yes	Yes	Yes	Yes	Yes	
Secondary 1: Intention- to-treat first pregnancy only	Yes	Yes	Yes	Yes	Yes	Yes	Yes	Yes	Yes	Yes	
Secondary 2: Per- protocol  /CACE	Yes	No	Yes	Yes	No	Yes	Yes	Yes	Yes	No	
Group=IVF			•	•		1	1	•			
	Conceived			Not conceived (		Conceived			Not conceived		
	IVF	With further intervention (IUI, IVF, FET)	Natural pregnancy	At least one IVF	No intervention	IVF	With further intervention (IUI, IVF, FET)	Natural pregnancy	At least one IVF	No intervention	
Primary: Intention-to- treat any pregnancy 	Yes	Yes	Yes	Yes	Yes	Yes	Yes	Yes	Yes	Yes	

Secondary 1: Intention- to-treat first pregnancy only	Yes									
Secondary 2: Per- protocol  /CACE	Yes	No	Yes	Yes	No	Yes	Yes	Yes	Yes	No

Yes=inclusion within analysis population (or considered adherent for CACE)

FET=Frozen embryo transfer

¹In the situation where e.g. an initial pregnancy did not result in a live birth ≥ 34 weeks, but a second one did then this outcome would supersede the result of the first pregnancy

<sup>2Per-protocol: only includes outcome relating to the randomised intervention (plus further intervention in the medium term period)

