## 15.2. Economic Analysis

A trial-based economic evaluation will be conducted to explore the relative cost-effectiveness of the two interventions. Given there is crossover anticipated between the interventions, as those allocated three cycles of IUI will be followed by the commencement of one cycle of IVF (though not before eight months has elapsed from randomisation), a model-based approach for analysing this may be most appropriate to capture the changes and crossover here, but we will explore whether this is necessary.

The appropriateness and feasibility of undertaking a distributional cost-effectiveness analysis will also be explored to address equity concerns around the distribution of costs and outcomes. This is a relatively new approach, and thus the feasibility of undertaking this analysis may be hampered by lack of availability of appropriate data.

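### The rule that IUI-arm couples wait until day 270 before IVF stands only in a note to the schedule table; Sections 7.1.1, 7.3 and 15.2 do not carry it

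*Protocol*

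**What the plan says.** Four places in the protocol bear on when a couple allocated to IUI may move to IVF.

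- **Section 7.1.1, Subsequent IVF** (treatment section): "all couples who are not pregnant after three cycles of IUI or 270 days (nine months) post-randomisation will be offered a cycle of IVF". Three unsuccessful cycles are enough to trigger the offer, and no earliest start is given.
- **Section 9.1, notes to the schedule table**: "All couples randomised to IUI cannot progress to subsequent IVF treatment until 270 days (approximately 9 months) post randomisation". This is the only statement of a bar at day 270.
- **Section 15.2, Economic Analysis**: IVF follows IUI, "though not before eight months has elapsed from randomisation".
- **Section 7.3**: "Any fertility treatment accessed by participants after completion of trial treatments is not considered a protocol deviation".

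The primary outcome (Section 8.2.1) is a live birth at 34 weeks or later from a conception within 270 days of randomisation. A fresh IVF conception is dated at egg collection, and "initial or subsequent pregnancies may be included within this timeframe". Table 9 has a column for IUI-arm conceptions within 270 days headed "With further intervention (IUI, IVF, FET"). It includes them in both intention-to-treat rows and excludes them from the per-protocol/CACE row. Section 1.1.4 says "we expect all couples unsuccessful after three cycles of IUI will proceed to at least one cycle of IVF".

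**The concern.** Day 270 does two jobs. It closes the conception window for the primary outcome, and under the schedule note it is the first day on which an IUI couple may go on to IVF. If the note is followed, no follow-on IVF conception can fall inside the primary window. If it is not, births from the comparator treatment enter the IUI arm's primary outcome.

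Counting such births is a deliberate treatment-policy choice and is not the problem. The problem is that the section describing the IUI strategy does not say whether the policy may include IVF before day 270, and Section 7.3 appears to excuse it. Sites could then deliver different policies under one label. In a non-inferiority trial, comparator births in the test arm move the result towards the conclusion the trial hopes to reach.

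**Working it through.** **1. Do the statements contradict each other?** Not strictly. Section 7.1.1 governs an offer, and an offer is not a start. Section 15.2 gives a lower bound, and any start from day 270 onwards also satisfies a bound of eight months. The schedule table places the follow-on IVF form at month 9. A reader holding all four passages can arrive at day 270. A reader holding only 7.1.1 and 7.3, or 15.2, cannot.

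**2. Could early IVF reach egg collection inside the window?** The protocol supplies the schedule (IUI forms at months 2, 4 and 6, described as approximate), the three-month limit for starting treatment (Section 7.1) and the 270-day window. My assumptions are 14 days from insemination to pregnancy test, 10 to 14 days of IVF stimulation, and no administrative delay.

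Egg collection day = day of third IUI + 14 + (10 to 14).

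| Third IUI cycle | Day | Egg collection | Room before day 270 |
|---|---|---|---|
| Month 6 (table schedule) | 183 | 207–211 | 59 to 63 days |
| Month 7 (first cycle at the three-month limit, same spacing) | 213 | 237–241 | 29 to 33 days |
| Month 8 | 243 | 267–271 | −1 to 3 days |

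The last column shows how much delay for consent, medication and booking the route can absorb. With 30 days of delay the month-6 route stays open (237–241) and the month-7 route nearly closes (267–271). With a full three months (about 91 days) even the month-6 route closes (298–302).

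**3. What does the eight-month figure allow?** 8 × 365.25/12 = 243.5 days, which is 270 − 243.5 = 26.5 days before the window closes. Stimulation begun then would reach egg collection at about day 253.5 to 257.5, inside the window. The two figures are therefore not interchangeable for the primary outcome.

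**4. Where would such a birth be counted?** In the IUI arm, in the primary intention-to-treat analysis (Table 9). It would be excluded from per-protocol/CACE, since Section 7.6 defines adherence as three cycles, or fewer if pregnant, "with no further fertility treatment in the IUI strategy group". Section 14.2 makes those analyses supportive.

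**5. How many couples does the rule govern, and what is one birth worth?** Using the planning rates in Section 14.1, the share unsuccessful after IUI is 1 − 0.18 = 82% at the margin and 1 − 0.28 = 72% if IUI matches IVF. With 471 × 0.9 = 424 evaluable couples per arm, that is 424 × 0.82 = 348 or 424 × 0.72 = 305 couples. One additional birth moves an arm's rate by 1/424 = 0.24 percentage points, against a margin of 10. The protocol gives no expected number of early IVF cycles, so the calculation stops here.

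**The case against.** The best reply is that the bar exists, is explicit and belongs to the same protocol. The schedule table agrees with it, and Section 15.2 explains an economic model and instructs no site. The timings in the working are a best case: Section 7.1 allows up to three months for treatment consent, medication and scheduling, and the schedule notes say the IUI cycles may take longer. Early IVF would also be visible. It is recorded on treatment forms, counts as non-adherent, is reviewed periodically by the oversight groups, and drops out of per-protocol/CACE.

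Most of this stands. It rules out calling the plan contradictory and makes frequent early IVF less likely. It does not put the rule where sites look for treatment instructions, and it does not remove the exemption in Section 7.3. Recording early IVF afterwards does not keep it out of the primary analysis.

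A reader might go further and infer that the trial's type I error is inflated. A figure can be produced. With 424 per arm and true rates of 18% for IUI alone and 28% for IVF, ten early IVF births in the IUI arm raise the chance of declaring non-inferiority from 2.5% to 12.4%. The documents do not support that as a finding, for two reasons. The ten births are assumed and one-sided: IVF-arm couples may have further frozen transfers within 270 days, Table 9 counts those conceptions too, and ten matching births return the figure to 2.5%. And 12.4% would be an error rate only for the effect of IUI alone. Under the treatment-policy contrast that the trial tests, an IUI policy that includes some early IVF has a truly higher birth rate, and the figure is power at that difference.

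**Conclusion.** The point holds as a gap in how the IUI policy is specified. The day-270 bar is operative only through a table note. The treatment section sets no minimum wait, Section 7.3 lets early IVF pass without a deviation, and Section 15.2 gives a date inside the primary conception window. The effect is on what the IUI policy comprises and on whether it is delivered alike across sites. Where it acts, it raises the IUI arm's rate for reasons other than IUI.

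The number of conceptions involved is unknown, and the net shift between arms cannot be derived from the documents. The conclusion rests on a site acting on 7.1.1 and 7.3 without the schedule note, and on the third IUI cycle and the IVF set-up being quick enough for egg collection by day 270. The sample size and the intention-to-treat approach are not in question. The change is worth making because the point touches the primary endpoint and the correction only applies the sponsor's own rule.

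**What to change.** Make three wording changes.

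- **Section 7.1.1**: state that one IVF cycle may be offered to couples not pregnant after three IUI cycles or at day 270, and that IVF stimulation must not start before day 270 after randomisation.
- **Section 7.3**: state that IVF started before day 270 in the IUI arm is a protocol deviation, and that such couples stay in follow-up and in the intention-to-treat analysis.
- **Section 15.2**: replace eight months with 270 days.

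Table 9 can stay as it is. The deviation form already exists, and no visits, forms or participants are added. Couples who finish IUI at month 6 would wait up to 270 − 183 = 87 days, but the schedule note already requires that. NHS age eligibility is not put at risk by the date itself: a partner providing eggs who is just under 39 at randomisation is about 39 + 270/365.25 = 39.7 at day 270, below the limit of 40 in Section 4.2. The protocol amendment itself is the only cost.
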